7.2.2 BLINDING

In order to minimize a source of bias, this trial is planned to be a double-blinded study. Research personnel performing the outcome assessments will be blinded to group allocation. Participants will be blinded of intervention.

7.3 VISIT 3 – 6 MONTH FOLLOW-UP VISIT

1. Blood Draw
2. Clinical Medical Questionnaire
3. Physical Activity Scale for the Elderly Questionnaire (PASE)
4. Montreal Cognitive Assessment (MoCA)
5. Geriatric Depression Scale (GDS-30)
6. Generalized Anxiety Disorder 7 (GAD-7)
7. Clinical Dementia Rating Scale (CDR)
8. Alzheimer's Disease Cooperative Study Activities of Daily Living (ADCS-ADL)
9. Physical Activity Readiness Questionnaire Plus (PAR-Q+)
10. Quality of Life Questionnaire (SF-36)
11. ADAS-Cog Plus Tests (ADAS-Cog 13 Tests, plus the Digit Span Forward and Backward WAIS-III, TMT A and B, Digit Symbol Test, Boston Naming Test)
12. D-KEFS Colour Word Interference Test
13. Short Physical Performance Battery (SPPB)
14. Six Minute Walk Test (6MWT)
15. Dual task control assessment while seated (mental task)
16. Gait assessment using Gait Mat and Accelerometers (when available)
17. Schedule Neuroimaging

7.4 TELEPHONE FOLLOW-UP (9 MONTH POST-BASELINE TESTING)

Three months after the end of the intervention, a telephone follow-up will take place to document any falls that have been recorded on the participants' falls calendar. This will be done by the study Site Coordinator or Research Assistant.

7.5 VISIT 4 – 12 MONTH FOLLOW-UP VISIT

1. Blood Draw
2. Clinical Medical Questionnaire
3. Physical Activity Scale for the Elderly Questionnaire (PASE)
4. Montreal Cognitive Assessment (MoCA)
5. Geriatric Depression Scale (GDS-30)
6. Generalized Anxiety Disorder 7 (GAD-7)
7. Clinical Dementia Rating Scale (CDR)
8. Alzheimer's Disease Cooperative Study Activities of Daily Living (ADCS-ADL)
9. Physical Activity Readiness Questionnaire Plus (PAR-Q+)
10. Quality of Life Questionnaire (SF-36)
11. ADAS-Cog Plus Tests (ADAS-Cog 13 Tests, plus the Digit Span Forward and Backward WAIS-III, TMT A and B, Digit Symbol Test, Boston Naming Test)
12. D-KEFS Colour Word Interference Test
13. Short Physical Performance Battery (SPPB)
14. Six Minute Walk Test (6MWT)
15. Dual task control assessment while seated (mental task)
16. Gait assessment using Gait Mat and Accelerometers (when available)

7.6 STUDY PROCEDURE DESCRIPTIONS

7.6.1 Clinical-Medical Questionnaires

The presence of chronic diseases, comorbidities, chronic medications, history of previous falls will be recorded. Whenever possible, a family member will be also interviewed in order to confirm the medical history and functional status. Finally, fear of falling will be assessed using the Falls Efficacy Scale and the fear of falling scale.

7.6.2 Functionality score

Self-reported information will be collected at baseline, six and twelve month's assessment on activities of daily living (ADLs) than are related to cognitive and physical capabilities. Specifically, the Alzheimer's Disease Cooperative Study Activities of Daily Living (ADCS-ADL) Inventory and IADL and Lawton Brody Instrumental Activities Of Daily Living (IADL) Scale will be used.

7.6.3 Blood Biomarkers

The following biomarkers will be drawn at the Baseline Visit, Visit 3 and Visit 4:

- Vitamin D levels, Calcium, PTH, and lipid level will be measured by conventional methods.
- Serum High Sensitive CRP, IL-6, BDNF, and VEGF receptor 1, IGF-1 will be determined by standardized ELISA methods

Blood samples for this study (completed at baseline and 6-month visit) will be done by a certified study Research Coordinator or Research Assistant. Participants will be asked to fast and will be provided with a small breakfast after the draw is complete. Samples will be collected, processed and stored securely at the respective site in a -80C freezer used for research purposes. Samples will be batch shipped securely to a centralized laboratory for analysis. Sample tubes will be labeled appropriately by the Study Coordinator with only the participant's unique study identifier and time point of collection.

7.6.4 Imaging

The imaging protocol will follow the *Canadian Dementia Imaging Protocol* developed for CCNA by [name], Laval University and colleagues, the latter having already been used by members of the *Consortium pour l'identification précoce de la maladie d'Alzheimer- Québec (CIMA-Q)* Pre-post regional patterns of brain plasticity will be assessed using structural (high-resolution 3D T1-weighted images = 7 min) in order to get voxel-based volumetric and cortical thickness measures, as well as diffusion tensor imaging (DTI, 30 directions, with AP/PA correction scan = 7 min) to calculate fractional anisotropy and diffusivity in white matter tracts as well as derive tract-based statistics. Cerebrovascular integrity and pathology will be assessed using the following contrasts: PD/T2 = 5 min; FLAIR = 7 min, and T2* = 5min). Functional magnetic resonance imaging at rest (rsfMRI plus field map = 12 min) will also be acquired to measure change in data-driven functional networks. Metabolite levels will be measured from the right motor cortex, cingulate cortex, and hippocampus, using single voxel spectroscopy. The total time for the scan session including scanning and patient setup is normally less than 1.5 hours.

7.6.5 COGNITIVE OUTCOMES

Alzheimer Disease Assessment Scale- Plus (ADAS-Cog Plus)

Global cognition will be assessed using the cognitive section of the Alzheimer Disease Assessment Scale Plus (ADAS-Cog Plus)[25]. The scale consists of 10 brief cognitive tests assessing memory, language, executive function and praxis. Scores range from 0 to 90, with higher scores indicating higher severity of cognitive impairment. The ADAS-Cog has been a significant outcome measure in numerous

trials with MCI and AD. The ADAS-Cog Plus has marked advantages as an outcome measure in MCI populations since incorporates items concerning executive function and functionality. Reliability and validity has been confirmed. Since several items are harmonized with the classical ADAS-Cog, it will also provide comparability with previous or existing trials assessing intervention in MCI. The ADAS-Cog Plus includes additional testing in executive function and caregiver reported functionality. Executive function of the ADAS-Cog plus is composed by the following tests: Trail-Making Test (TMT) A & B, the WAIS-R Digit Symbol Substitution Test (DSST), Digit Span Test, and Category Fluency.

In brief, The TMT (A & B) assesses attention, speed, and mental flexibility. For this test, participants connect numbers (TMT-A) and numbers and letters (TMT-B) in order. Time to complete is the outcome of interest for this measure. Trails A is truncated at 3 min and Trails B at 5 min. The DSST measures speed and information processing. Participants are instructed to refer to a number-symbol key at the top of the page and to write the appropriate symbols under the corresponding numbers as quickly as possible. For the Digit Span Test, an auditory attention task, participants are asked to recall a series of numbers forward and backward. For Category Fluency, a measure of speed and flexibility of verbal thought, participants are asked to name as many items as possible in a specified category (vegetables); unique responses during the first minute were counted. Functionality will be assessed by the following five functionality questions : 1) “Ability of writing checks, paying bills, balancing checkbook;” 2) “Assembling tax records, business affairs, or papers”; 3) “Playing a game of skill, working on a hobby;” 4) “Keeping track of current events;” and 5) “Remembering appointments, family occasions, holidays, medications.”

Trail Making Test (TMT) A & B (s)

The Trail Making Test (TMT) measures set shifting abilities. Both parts of the test consist of 25 circles distributed across a sheet of paper. For the first portion of the test (TMT A), the participant is required to draw lines to connect numbers in ascending order as quickly as possible. This part assesses visual perception and psychomotor rapidity. TMT B assesses mental shifting and the participant’s attention ability, as they are required to do the same task as for TMT A, but alternating between numbers and letters. The participant is asked to perform the task as quickly as possible without lifting his/her pen from the paper. If the experimenter sees a mistake, she/he informs the participant. Results for both TMT A and B are reported as the number of seconds required to complete each task; therefore, higher scores reveal greater impairment. Trail A \leq 40 seconds and Trail B \leq 90 seconds are considered normal average values for these tests for older adults in the range of 60 to 75 years old. To index set shifting, the

difference between part B and part A completion times, smaller difference scores indicate better set shifting. [46]

Digit Span Test WAIS-III (Forwards & Backwards)

These tests measure short term and working memory. For the Digit Forward, participants are instructed to listen to each series of numbers in completion, followed by repeating the numbers in the same order. The final score is the sum of points from each correct trial. The maximum score is 16. For the Digit Backward, participants are instructed to listen to each series of numbers in completion, followed by repeating the numbers in the backward order. The final score is the sum of the points from each correct trial/series, with a maximum score of 14. The difference between the Digit Span Forward and Backward test scores is used as an index of the central executive component of working memory. Smaller difference scores indicate better working memory.[47,48]

Boston Naming Test

This test measures confrontational word retrieval skills. This version is composed by thirty pictures that are shown by the experimenter one by one. Participants are asked to name verbally each of the 15 nouns depicted in the black and white drawings. Following an error in naming, a semantic and/or phonemic cue is provided verbally to participants wherein the participants are given up to 20 seconds to respond following each cue. This task will be digitally recorded and stored. If the participant is not able to retrieve the name even after the semantic cue the experimenter gives a phonemic cue by speaking the part in bold (e.g. scroll; Experimenter says: “sc”).

Generalized Anxiety Disorder 7 (GAD-7)

The Generalized Anxiety Disorder 7 is a self-rated measure of anxiety symptoms and its score is calculated by rating 0, 1, 2, and 3 to the response categories of “not at all”, “several days”, “more than half the days” and “nearly every day”, respectively, and adding together the scores for the seven questions. A score of 10 or higher has a sensitivity of 89% and a specificity of 82% for generalized anxiety disorder; a score of 5 is considered the cut-off for “mild” anxiety and 15 for “severe” anxiety.⁴⁵

Geriatric Depression Scale (GDS-30)

The Geriatric Depression Scale was designed to discriminate the pattern of depressive symptoms from the general characteristics of the elderly population. It is a brief 30-item questionnaire in which participants are asked to respond by answering yes or no in reference to how they felt over the past week. The GDS was found to have a 92% sensitivity and a 89% specificity when evaluated against diagnostic criteria. Cut-off: normal-0-9; mild depressives-10-19; severe depressives-20-30.[49]

Mini Mental State Examination (MMSE)

A 30 point questionnaire used to assess mental status. The MMSE tests 5 areas of cognitive function: orientation, registration, attention and calculation, and recall and language.

Montreal Cognitive Assessment Test (MoCA)

The Montreal Cognitive Assessment (MoCA) was designed as a rapid screening instrument for mild cognitive dysfunction. It assesses different cognitive domains: attention and concentration, executive functions, memory, language, visuoconstructional skills, conceptual thinking, calculations, and orientation. Time to administer the MoCA is approximately 10 minutes. The total possible score is 30 points; a score of 26 or above is considered normal. [41]

7.6.6 MOBILITY OUTCOMES

Gait velocity and variability (single and dual-tasking)

Gait velocity will be assessed as the time taken to walk the middle 6 meters of 8 meters using the Portable Walkway System (ProtoKinetic® and/or GAITRite® Systems, Inc.) These devices automate the acquisition, analysis, and reporting of the objective parameters of gait as the subject walks down the walkway with embedded sensors. As a result, these gait mats allow detecting subtle changes in gait, including gait variability since it has been proven to have a fine discrimination when compared with other quantitative methods.[50] The gait mat is located in a well-lit room with start and end points marked on the floor one meter from either end of the mat to avoid recording acceleration and deceleration phases.

Instrumentation:

Gait performance will be assessed using electronic walkway systems (GAITRite® or PkMas®), which automatically determines spatiotemporal gait parameters from imbedded sensors activated by foot pressure. A computer processes the footsteps, providing data for both spatial and temporal parameters. In addition, among sites without electronic walkway systems, quantitative gait parameters will be assessed using wearable inertial sensors (Gulf Coast Inc.; Shimmer Inc.) worn bilaterally on the ankles and at the hip. Acceleration data will be used to calculate foot-contact and foot-off times determine step and stride timing data. Overall gait velocity is determined by timing the standard walk distance.

For walking conditions all individuals will perform walks along a 6 meter path while wearing hip and ankle worn accelerometers. Individuals will perform three main tasks: 1) preferred walking speed, 2) dual task walking and 3) fast walking. In the case that a participant uses an assistive aid (cane, walker), the tester will determine the participant's capacity to walk safely without the use of the aid. With the

willingness of the participant, they will then perform one test walk without the use of the aid. If the participant is able to safely walk without the use of the assistive aid, all subsequent testing will be performed without its use. In all walks, participants will start 1 meter before the beginning of the 6 meter platform and continue to travel 1 meter past the end of the platform. This procedure is in place to ensure steady-state walking and to minimize any effects of acceleration and de-acceleration during the course of the walk.

The first walking block will measure self-selected or preferred walking. Participants will be instructed to “walk at a comfortable and secure pace”. For preferred walking speed, a total of three walks will be performed. Participants with slow walking speed, less than 0.6m/s, or participants with lower limb disability, will be allowed to complete one walk if they are not able to perform the three trials. We require a minimum of approximately 20-steps to allow measurement of step-to-step variability. For example, an individual who walks at 1.5 m/s would usually only have 4-5 steps per walk. Therefore, we would need at least 3 repetitions. For those walking less than 1.0 m/s, two trials is commonly necessary. For those walking less than 0.5 m/s, a single walk is usually sufficient.

The second walking block will be dual-task walking and includes three separate walks. Before performing the walking task, participants will enumerate out loud the verbal outputs will be performed from a seated position prior to any walks and recorded. The seated assessments will be timed at 10 seconds for dual-tasks and will be performed in the beginning of all cognitive assessments to prevent practice effects in dual-task gait performance (see order of assessments for visit 2, 3 and 4). If during the assessment time restriction appears or the assessor can see the tasks are difficult for the individual, the minimum gait assessment required will be usual gait, naming animals and Serial 7s. The first dual-task administered will have the participant walk on the platform while simultaneously counting backward by serial 1's from 100 (100-99-98...) out loud. The second dual-task will have the participant repeat the walk but this time, while naming animals (fluency test). In the third dual-task, the participant will be asked to walk the platform while subtracting 7's from 100 (100-93-86...) out loud. During this trial, participants are encouraged to keep walking even if they cannot do the subtractions. These dual-task conditions selected are based on previous research which demonstrated that counting backwards requires both working memory and attention[51]. Participants will be instructed to pay attention to both gait and the cognitive task; if a participant stops either task during the trial, they will be prompted to continue. Not instructing to prioritize gait over cognitive task or vice-versa allows both gait and cognitive task to vary. This has previously been shown to provide a better representation of what happens naturally [52,53]. The evaluator will record any counting errors during walking.

The third and last walking block will include fast walking and the participants will be instructed to walk as fast and safe as they can without running.

Six-minute Walking Test (6MWT)

The 6MWT is used to quantitatively measure participants' exercise capacity by measuring the maximum distance that a person can walk in 6 minutes. The test is a modification of the 12-min walk/run test originally developed by Cooper [54] and is commonly used as an assessment of exercise capacity. The 6MWT is useful for predicting the maximal oxygen uptake related to cardiorespiratory fitness and is easily administered in clinical settings [55]. The 6MWT is believed to be a useful instrument because of its ease of administration and similarity to normal daily activities. It is a submaximal test of aerobic capacity which has been successfully used in MCI populations [56].

The 6MWT will be assessed by licensed and trained physical therapists. The participants are instructed to walk from one end of a 10-meter course to the other and back again as many times as possible in 6 min, while under the supervision of a physical therapist. After each minute, participants were informed of the time elapsed and were given standardized encouragement. The distance (meters) walked in 6 min was recorded [55].

Short Physical Performance Battery (SPPB)

It is a widely used instrument for quantifying lower extremity function and mobility in older adults. It is a group of measures that combines the results of the gait speed, chair stand and balance tests [57]. It has been used as a predictive tool for possible disability and can aid in the monitoring of function in older people. The scores range from 0 (worst performance) to 12 (best performance). The SPPB has been shown to have predictive validity showing a gradient of risk for mortality, nursing home admission, and disability. [58]

7.6.7 FUNCTIONAL OUTCOMES AND COMBINED SCORE OF COGNITION AND FUNCTIONALITY (POOLED INDEX)

Functional Outcomes: Activities of daily living and everyday function will be evaluated using the use the ADCS which is a 23-item informant-rated questionnaire that measures, in a range of 0 to 78, an individual's performance of activities of daily living.

Pooled Index: A pool index including measures of cognition, mobility and functionality will be used as a secondary outcome. The cognitive decline seen with aging, due to neurodegenerative or vascular mechanisms, affects not only cognition but also mood, behavior and the ability to perform activities of

daily living. Therefore, treatments are considered successful if they slow down the progression of cognitive decline and maintain functionality and independency. Studies conducted in psychiatric patients and therapies for rheumatoid arthritis have demonstrated the applicability of a pooled index (PI) in measuring overall function and how changes in PI scores can be analyzed to quantify improvement or worsening conditions over time[60-62]. To apply this approach in our cohort, we constructed the **Cognition and Functionality Pooled Index** with six continuous variables sensitive to cognition function in older adults: Trail- Making Test, parts A and B (executive function), Rey Auditory Verbal Learning Test (RAVLT) (semantic memory, verbal learning), Geriatric Depression Scale [GDS] (mood), Alzheimer's disease Activities of Daily Living-International Scale [ADL-IS] (functionality), and dual-task gait cost. The efficiency of a Pool Index is greatest when the combined variables are poorly correlated ($r<0.4$) which reduces variance of PI. The suitability of our 6 source variables was confirmed by calculating the strength of pairwise correlations using Pearson Correlation Coefficient. The pooled index is created by converting all individual scores from the six tests to standardized z scores by subtracting the baseline group mean and dividing by the baseline group SD, and then averaging the standardized z scores. For tests with more than 1 component, the component scores were first averaged to create a single z score for each test (e.g., z scores for Trails A and B were averaged to create a single Trails z score) so that all tests were weighted equally, and then the mean z scores for the 6 tests was calculated.

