	WAIS III digit forward and backward
	Category fluency – Animals and Vegetable

119 **9. Secondary Outcomes^{*}**

120 Secondary outcomes include neuropsychological assessments, gait and mobility
121 outcomes (including incidence of fall), neuroimaging, and blood biomarkers. *Note that
122 secondary outcomes will be not reported in the primary manuscript.

123 **9.1 Change in cognitive function on neuropsychological tests**

124 The secondary cognitive outcomes will include:

125 a) Montreal Cognitive Assessment test for global cognition
126 b) The ADAS-Cog Recall word list for verbal semantic memory
127 c) Trail Making Test A and B
128 d) Digit Symbol Substitution Test
129 e) Digit Span Test Forward and Backwards
130 f) Boston Naming Test
131 g) Verbal fluency Animals and Vegetables

132 **9.2 Change in gait performance**

133 Gait performance will be evaluated using gait speed and gait variability under single and
134 dual-tasking. Gait speed will be measured as the time taken to walk 6 m using an
135 electronic walkway system (ProtoKinetic® and/or GAITRite® Systems, Inc.). Gait
136 variability of spatial and temporal gait variables (stride time, stride length, double
137 support time and step width) will be calculated using the coefficient of variation (CV =
138 (standard deviation / mean) ×100).

139 **9.3 Change in mobility and falls**

140 Mobility will be measured with the Short Physical Performance Battery (SPPB), and the
141 6 min walk test (6MWT).

142 A fall will be defined as 'unintentionally coming to rest on the ground, floor, or other
143 lower level and not due to a seizure, syncope, or an acute stroke'. Recurrent falls are
144 defined as 'two or more events in a 12-month period'. Falls will be recorded throughout
145 the 12-month trial, participants will be provided with a falls calendars, on which they will
146 record any falls that have occurred, and they will be asked to bring them monthly to the
147 training sessions to review with a research staff member. After the completion of the
148 intervention, participants will be contacted at month 9 and 12 to report incidental falls.

149 **9.4 Change in Neuroimaging**

150 Pre-post regional patterns of brain plasticity will be assessed using structural (high-
151 resolution 3D T1-weighted images = 7 min) in order to get voxel-based volumetric and
152 cortical thickness measures, as well as diffusion tensor imaging (DTI, 30 directions, with

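### The Pooled Index averages z-scores without aligning their directions, names two instruments that no visit schedules, and counts five tests as six

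*Combined protocol and SAP*

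**What the plan says.** Protocol section 7.6.7 names the Cognition and Functionality Pooled Index as a secondary outcome and describes it as "six continuous variables sensitive to cognition function in older adults". The components are Trail Making A and B, "Rey Auditory Verbal Learning Test (RAVLT) (semantic memory, verbal learning), Geriatric Depression Scale [GDS] (mood"), and then the Alzheimer's disease "Activities of Daily Living-International Scale [ADL-IS] (functionality), and dual-task gait cost".

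The recipe is complete in form. It consists of "converting all individual scores from the six tests to standardized z scores by subtracting the baseline group mean", dividing by the baseline SD, and averaging. Tests with several parts are averaged first, to give each test equal weight; the example is that "z scores for Trails A and B were averaged to create a single Trails z score". The mean is then taken over what the section calls six tests. The section also says that the source variables were checked for low pairwise correlation, with r below 0.4 as the mark.

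On direction, section 7.6.5 says of Trails times: "therefore, higher scores reveal greater impairment". Its GDS cut-offs run from normal (0-9) to severe (20-30).

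The SAP does not mention the index. Its section 9.1 lists "The ADAS-Cog Recall word list for verbal semantic memory" and no RAVLT. Its section 10.3 leaves the secondary analyses to a later plan.

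**The concern.** An average of z-scores measures benefit only if every z-score points the same way. Here at least two components (Trails, GDS) go down when a participant improves. The ADL scale described in the same section is framed as performance on a 0 to 78 range, which implies that it goes up. Nothing in the recipe turns either group round, so gains on one side offset gains on the other, and a high index value has no defined meaning.

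Two further points concern whether the index can be put together at all. RAVLT and ADL-IS are named components, but neither is scheduled anywhere. The stated number of tests also does not match the list once Trails A and B are merged.

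Section 7.6.7 is the only definition of this outcome. If it stands, the direction rule, the replacement instruments and the divisor will be chosen outside the plan, possibly after data have been seen.

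**Working it through.** **1. Count of tests.** With Trails A and B separate: Trails A, Trails B, RAVLT, GDS, ADL-IS, dual-task gait cost = 6 variables. This reproduces the six variables stated. After the prescribed merge: Trails, RAVLT, GDS, ADL-IS, dual-task gait cost = 5 tests. The stated six tests is not reproduced.

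**2. Are the components scheduled?** The places checked were protocol sections 7.1, 7.2, 7.3 and 7.5, Appendix I, and SAP Table 1.
- Trails, GDS and the gait assessments (the source for dual-task cost) are listed.
- RAVLT is in none of them. It appears only in the abbreviations, the index definition and the reference list.
- ADL-IS is in none of them. The ADL scales listed are ADCS-ADL and the Lawton-Brody IADL.

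**3. Direction of each component.**
- Trails: higher = worse (section 7.6.5).
- GDS: higher = worse (cut-offs in 7.6.5).
- ADL: higher = better is implied for the ADCS (7.6.7). No direction is given for ADL-IS, so both are shown below.
- RAVLT: not stated; assumed higher = better.
- Dual-task gait cost: not defined; assumed higher = worse.

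**4. Movement of the unaligned index.** Suppose every test improves by d SD (an assumption; the plan gives no effect size for the index). Let s = -1 where higher is worse and +1 where higher is better. Shift = d × (sum of s) / m for m tests. Share cancelled = 1 - |sum of s| / m. With all signs aligned, the shift is 1.0d.

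| Reading | Signs | Shift | Cancelled |
|---|---|---|---|
| Five tests, ADL higher = better | -1 +1 -1 +1 -1 | -0.2d | 80% |
| Four tests, no RAVLT, ADL higher = better | -1 -1 +1 -1 | -0.5d | 50% |
| Five tests, ADL higher = worse | -1 +1 -1 -1 -1 | -0.6d | 40% |
| Four tests, no RAVLT, ADL higher = worse | -1 -1 -1 -1 | -1.0d | 0% |

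With d = 0.5, the first row gives -0.10 SD and the second -0.25 SD, against 0.50 SD aligned.

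**5. The divisor.** Dividing the five-test sum by 6 gives -1/6 = -0.167d in place of -0.2d. Every participant's score, and hence the SD, shrinks by the same factor 5/6. The standardised effect and the p-value do not change.

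**6. Illustration of power, first row only.** Assume d = 0.5, unit component SDs, equal correlation ρ between aligned components, 34 per arm (protocol 5.3) and two-sided 0.05 (protocol section 8).
- Aligned variance of the index = (5 + 20ρ)/25; unaligned = (5 - 4ρ)/25.
- Power = Φ(|effect|/SD × √(34/2) - 1.96).
- At ρ = 0, 0.2 and 0.4 the aligned standardised effects are 1.118, 0.833 and 0.693, with power 99.6%, 93% and 82%.
- The unaligned effects are 0.224, 0.244 and 0.271 in size, with power 15%, 17% and 20%.

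**The case against.** The best case for the plan has four parts.

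*Silence is not a ban on sign reversal.* Section 7.6.7 says that changes in pooled-index scores can show patients getting better or worse, which presupposes a common direction, and it cites methods papers that are not part of these documents. A competent programmer might align the signs unasked. This has some force as to intent. But the section sets out every step of the score, and a reversal is not among them.

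*The size of the loss is mostly assumed.* This stands. The documents give a direction for Trails and GDS only, and imply one for the ADCS. A reader might infer that half to four-fifths of a real effect is lost. The documents do not support that as a fact: across the readings the loss runs from 0% to 80%, and every figure assumes equal gains on all tests.

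*The schedules are not exhaustive.* Section 7.6.9 requires a health resource utilization questionnaire at Visits 2 and 3 that no visit list or table shows, and the Envelope Test is in Appendix I but in no visit list. So a reader should not infer from the schedules that RAVLT was certainly never given. What stands is that nothing schedules RAVLT or ADL-IS, and SAP 9.1 assigns verbal semantic memory to a different test. The index cannot be assembled from the scheduled tests.

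*The miscount does no harm.* This also stands as far as signal goes: it is a constant rescaling. It remains an inconsistency to correct.

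**Conclusion.** The point holds as a defect in the definition of a secondary outcome. Three parts need no assumption: the recipe has no direction rule although Trails and GDS rise with worsening, RAVLT and ADL-IS are unscheduled, and five tests are called six.

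The size of the cancellation is conditional. It is 80% for the five tests as written, or 50% without RAVLT, if RAVLT and ADL are higher = better and dual-task cost is higher = worse. It is 40% or 0% if the ADL scale runs the other way. Only the missing sign reversal causes it; leaving RAVLT out reduces it, and the count has no effect on it.

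A reader might go further and doubt the trial's main result. The documents give no ground for that: neither the primary outcomes, their analysis nor the sample size uses this index. It should be corrected before the secondary analyses, because no later document does so.

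**What to change.** Amend the definition and carry it into the secondary-outcome analysis plan before those analyses are run:

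- State the direction of each component and reverse signs so that higher means better throughout.
- Name only collected instruments. Use ADCS-ADL in place of ADL-IS. For RAVLT, either drop it or use ADAS-Cog word recall, direction-aligned. Word recall is an item of both primary outcomes (SAP Table 2), so that overlap should be acknowledged.
- Recheck the r < 0.4 criterion on the revised set, since the reported check covered a set that includes the unscheduled instruments.
- State the true number of tests (five with word recall, four if RAVLT is dropped) and use it as the divisor.
- Say whether the baseline mean and SD come from all participants or from each arm.

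The cost is a little wording and programming. The substitutes named are already in the visit schedules, so no new assessment is needed. The one trade-off is some overlap with the primary outcomes if word recall is used.
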